11. STATISTICAL CONSIDERATIONS

The primary objective of the study is to evaluate the PK and safety profile of multiple doses of NT-814 compared to placebo by daily administration of each dose for 14 days. No primary hypothesis test is pre-specified for this Phase I study.

11.1 Estimated sample size

The planned sample size is 20 subjects per cohort, with 15 active and 5 placebo. This is deemed enough to provide sufficient separation of exposures between dose groups and to allow for an assessment of safety versus dose group/exposure. Assuming a standard deviation on the log scale of 0.413 for plasma AUC₀₋₂₄ (based on Day 7 mean AUC₀₋₂₄ data for 200 mg from study MNK111857), 15 active subjects per cohort provides close to 80% power at a type I error rate of 0.1 to detect a difference from one in the ratio of geometric means between the two highest possible dose levels (and greater than 90% power for the middle two dose levels) given the previously seen slightly greater than dose proportionality increase in systematic exposure. The placebo subjects are included primarily to provide a reference group for comparison of safety in the target population.

11.2 Analysis sets

The following data sets will be used for the statistical analysis.

1. **Safety Set:** All subjects who receive at least one dose of double-blind study drug. Subjects will be analyzed according to treatment received.
2. **Pharmacokinetic (PK) Set:** all subjects who received at least one dose of active study drug and for whom the PK data are considered sufficient.
3. **Full Analysis Set (FAS):** All randomized subjects who received at least one dose of double-blind study drug and for whom the efficacy data are considered sufficient and interpretable. Subjects will be analyzed according to randomized treatment.

Analysis Sets will be identified prior to the unblinding of the study data.

11.3 Data analysis

More details of the proposed statistical analysis will be documented in the statistical analysis plan (SAP), which will be written following finalization of the protocol and finalized prior to the breaking of the blind. PK, safety and efficacy data will be presented by means of descriptive statistics and figures, as appropriate, by treatment. Data for the placebo subjects will be combined across cohorts prior to any summaries.

Summary statistics will be based primarily on non-missing values.

Full details on the handling of missing values, including rules applied to incomplete questionnaires (including incomplete diary entries) will be defined in the SAP.

Raw data will be listed.

11.3.1 Baseline assessment

Descriptive statistics will be performed on relevant screening and baseline data (i.e. data collected prior to the treatment administration) and on demographic characteristics for each treatment group.

11.3.2 Safety analysis methodology

The safety and tolerability profile will be assessed versus baseline conditions and differences between treatment groups and descriptive statistics will be produced, where applicable.

A treatment-emergent analysis will be done for AEs. AEs will be tabulated by MedDRA preferred term and system organ class. Tabulations by severity and drug-relatedness will also be made.

A concentration-effect model will be built investigating ECG assessments versus plasma concentrations.

Extent of exposure and compliance will be evaluated.

11.3.3 Pharmacokinetic analysis methodology

Plasma concentration versus time data for NT-814 will be evaluated by standard non-compartmental analysis using appropriate software. Individual plasma concentration versus time profiles for each subject and mean and median plasma concentration versus time profiles by dose will be generated. The following PK parameters will be log-transformed prior to statistical analysis: AUC_{0-t} , $AUC_{0-\tau}$, $AUC_{0-\infty}$, C_{max} , CL/F , and $t_{1/2}$.

For each of the parameters the following summary statistics will be calculated and tabulated by treatment: n, arithmetic mean, 95% CI (confidence interval) for the arithmetic mean, standard deviation, minimum, median, maximum, geometric mean, 95% CI for the geometric mean, and standard deviation of log-transformed data. Between-subject coefficient of variation (%CVb) will also be calculated.

For t_{max} , t_{lag} , n, median, minimum, maximum, arithmetic mean, 95% CI for the arithmetic means and standard deviation will be calculated.

Accumulation and time invariance will be evaluated by comparisons of Day 1 AUC_{0-24} versus Days 7 and 14 and Day 1 $AUC_{0-\infty}$ versus AUC_{0-24} Days 7 and 14 respectively.

Dose proportionality will be assessed on Day 7 (AUC_{0-24} and C_{max}).

11.3.4 Exploratory analyses

Analysis of efficacy data will be primarily descriptive. Derivations of the efficacy endpoints will be provided in the SAP. Exploratory dose response and PK-PD analyses may be conducted. Any statistical hypothesis tests and/or confidence intervals will be two sided, using a type I error rate of 0.1. No adjustments will be made for multiplicity in this early phase study.

11.4 Study specific data analysis

At the end of each Cohort a blinded review of PK and safety data will be conducted by the Principal Investigator, Medical Monitor and Sponsor team to confirm whether it is considered safe to continue to the subsequent dose. Dose escalation will not occur if the exposure of NT-814 is predicted to exceed a geometric mean AUC of 20950 ng.h/mL (2-fold safety margin).

In the case of an ambiguous decision, all data may be unblinded to help with the dose escalation decisions.

12. END OF THE STUDY

The end of the study will be defined as the last subject's last visit.

13. IRB REVIEW/INFORMED CONSENT

13.1 Institutional Review Board (IRB) and relevant authorities

The final study protocol and the subject information and consent form will be approved by an appropriately constituted independent Institutional Review Board (IRB). Approval will be received in writing before initiation of the study.

Clinical Trial Authorization will be obtained prior to initiation of the study from the U.S. Food and Drug Administration (FDA).

13.2 Ethical conduct of the study

The study will be performed in accordance with the local regulations, the principals of Good Clinical Practice (GCP) as described by the International Council for Harmonization (ICH), and the ethical principles that have their origins in the Declaration of Helsinki.

13.3 Informed consent

For each study subject, written informed consent will be obtained prior to any protocol-related activities. As part of this procedure, the principal investigator or one of his associates will explain orally and in writing the nature, duration, purpose of the study, and the action of the study drug in such a manner that the subject is aware of the potential risks, inconveniences, or adverse effects that may occur. They will be informed that their medical records may be reviewed by appropriately qualified monitors of the Sponsor or Sponsor Representative, and by auditors or regulatory authorities to ensure the accuracy of the details recorded as part of the study. They will be informed that they may withdraw from the study at any time without prejudice to further

treatment. They will receive all information that is required by local regulations and ICH guidelines.

14. STUDY AND DATA MANAGEMENT

14.1 Protocol amendments

Once approved by the applicable Regulatory Authorities and IRBs, the protocol must not be amended without approval by NeRRe. Unless an amendment is required to be implemented urgently in the interests of safety, any amendments to the protocol must be authorized by the applicable Regulatory Authorities and IRB prior to implementation.

14.2 Monitoring

In accordance with applicable regulations including GCP and NeRRe or delegated CRO's Standard Operating Procedures (SOP), approved clinical research monitors will contact the site prior to the start of the study to review with the site staff the protocol, study requirements, and their responsibilities to satisfy regulatory, ethical, and NeRRe requirements. When reviewing data collection procedures, the discussion will also include identification, agreement and documentation of data items for which the eCRF will serve as the source document. A list of what is to be classed as 'source documentation' will be documented in the Study Monitoring Manual.

NeRRe will monitor the study and sites to verify that the:

- Data are authentic, accurate and complete.
- Safety and right of the subjects are being protected
- Investigational Product accountability
- SAE reporting
- Study is conducted in accordance with the currently approved protocol and any other study agreements, GCP and all applicable regulatory requirements.

The Investigator agrees to allow the monitor direct access to all relevant documents.

14.3 Quality assurance

To ensure compliance with GCP and all applicable regulatory requirements, NeRRe may conduct a quality assurance audit. Regulatory agencies may also conduct a regulatory inspection of this study. Such audits/ inspections can occur at any time during or after completion of the study. If an audit or inspection occurs, the Investigator and institution agree to allow the auditor/ inspector direct access to all relevant documents and to allocate his/ her time and the time of his/ her staff to the auditor/ inspector to discuss findings and any relevant issues.

14.4 Data recording

14.4.1 Case report form

An eCRF will be used to capture subject data. Access to enter data in the eCRF will be limited to delegated and trained investigator site staff only.

100% of data in the eCRF will be source data verified by monitors.

14.5 Confidentiality

Study data will be handled with utmost discretion within the context of physician's confidentiality. On the eCRFs and other study specific documents, subjects are not identified by their names, but by a unique subject number. Names of participating subjects and data generated as a result of this study will not be passed on to unauthorized persons.

The Investigator must assure that the subjects are properly anonymized throughout the study. On all study documentation which is supposed to leave the site (i.e., to be transmitted to NeRRe, CRO or third parties), subjects will only be identified by their unique identification code and will not be referred to by name.

NeRRe may transfer some data collected during the study to a different company or regulatory authority outside of the US for the purpose of processing, review, analysis or storage. Whenever the subject's personal data is transferred, it will be kept confidential and secure, and will used only for the purpose for which it was collected.

Safety analysis samples collected during the study will be analyzed at the local hospital facility per local procedures. As such samples will not be leaving the local hospital laboratory facility; there will be no specific study requirements to make the samples anonymous. All safety samples will be destroyed after the assays have been completed.

NT-814 PK samples will be shipped to Aptuit Srl, Italy for analysis. Analysis will be conducted after each cohort with the results included in the final study report. Following completion of the analysis, all samples will be destroyed.

14.6 Retention of study data

Following closure of the study, the Investigator must maintain all site study records, except for those required by local regulations to be maintained by someone else, in a safe and secure location. The records must be maintained to allow easy and timely retrieval, when needed (e.g., audit or inspection), and, whenever feasible, to allow any subsequent review of data in conjunction with assessment of the facility, supporting systems, and staff. Where permitted by local laws/ regulations or institutional policy, some or all of these records can be maintained in a format other than hard copy (e.g., microfiche, scanned, electronic); however, caution needs to be exercised before such action is taken. The Investigator must assure that all reproductions are legible and are a true and accurate copy of the originals, and meet accessibility and retrieval

standards, including re-generating a hard copy, if required. Furthermore, the Investigator must ensure there is an acceptable back-up of these reproductions and that an acceptable quality control process exists for making these reproductions.

NeRRe will inform the Investigator of the time period for retaining these records to comply with all applicable regulatory requirements. The minimum retention time will meet the strictest standard applicable to that site for the study, as dictated by any institutional requirements or local laws or regulations, or NeRRe, or delegated CRO's SOPs; otherwise, the retention period will default to 15 years.

The Investigator must notify NeRRe of any changes in the archival arrangements, including, but not limited to, archival at an off-site facility or transfer of ownership of the records in the event the Investigator leaves the site. The Investigator may not dispose of any records without prior approval from NeRRe.

14.7 Communication and publication of results

Where required by applicable regulatory requirements, an Investigator signatory will be identified for the approval of the clinical study report (CSR). The Investigator will be provided appropriate access to statistical tables, figures, and relevant reports and will have the opportunity to review the complete study results at NeRRe or another mutually agreeable location.

The original eCRFs and all data generated during the study under this protocol will become the property of the Sponsor.

Upon completion of the CSR, NeRRe will ensure public disclosure of the clinical trial research results according to the NeRRe's SOP and provide the Investigator with the full summary of the study results. The Investigator is encouraged to share the summary results with the study subjects, as appropriate.

It is the intent of all parties that the results of the study be published in a timely manner consistent with academic standards and with due consideration given to the protection of intellectual property rights. The Principal Investigator and NeRRe will be responsible for assembling the proposed publication; this must happen with due diligence and with minimal delay.

Any proposed publication or presentation (including a manuscript, abstract or poster) for submission to a journal or scientific meeting should be sent to the Sponsor for review at least one month prior to submission. The Sponsor's comments on the proposed publication shall be considered in good faith by the authors. Sponsor may delay such submission by a maximum of ninety (90) days if it reasonably believes that publication of results may compromise its intellectual property rights or else insist that such information or data is removed from the proposed publication. Publication of the results will not include confidential information without the permission of the Sponsor.

14.8 Indemnification

In the event of study-related damage or injuries, the clinical trial insurance of the Sponsor provides compensation for claims that arise in accordance with the regulatory requirements of the countries involved, except for claims that arise from willful misconduct or gross negligence. A copy of the country-specific insurance certificates will be held in the TMF and in the Investigator site file.

1 LIST OF ABBREVIATIONS AND DEFINITIONS OF TERMS

Abbreviation or Specialist Term	Explanation
ACTH	adrenocorticotrophic hormone
AE	adverse event
AUC	area under the concentration-time curve
AUC ₀₋₂₄	AUC from time 0 to 24 hours
AUC ₀₋₈	AUC from time 0 to 8 hours
AUC _{0-∞}	AUC from time 0 to infinity
AUC _{0-t}	AUC from time 0 to the time of the last quantifiable concentration
AUC _{0-τ}	AUC during a dosage interval
BP	blood pressure
CI	confidence interval
C _{max}	maximum observed concentration
CPU	Clinical Pharmacology Unit
CRF	case report form
CYP	cytochrome P450
DMP	Data Management Plan
ECG	electrocardiogram
eCRF	electronic case report form
FSH	follicle stimulating hormone
HR	heart rate
ICH	international conference on harmonization
IMP	investigational medicinal product
LH	luteinizing hormone
MedDRA	medical dictionary for regulatory activities
N.B.	nota bene
No.	number
NTA	night time awakening
PK	pharmacokinetic

PR	atrioventricular nodal delay
PT	preferred term
QD	once daily
QRS	ventricular depolarization
QT	electrical depolarization and repolarization of the ventricles
QTcB	corrected QT by Bazett's formula
QTcF	corrected QT by Fridericia's formula
RR interval	time between heart beats used to calculate heart rate
SAE	serious adverse event
SAP	Statistical Analysis Plan
SD	standard deviation
SE	standard error
SOC	system organ class
TEAE	treatment-emergent adverse event
T3	triiodothyronine
T4	thyroxine
t _{1/2}	terminal elimination half-life
T _{max}	the time that C _{max} was observed
TSH	thyroid-stimulating hormone

2 INTRODUCTION

This statistical analysis plan (SAP) is consistent with the statistical methods section of the study protocol (version 4.0 dated 13 December 2016) and includes additional detail of safety and efficacy summaries to be included in the clinical study report. The bioanalyses will be performed by Aptuit Medicines Research Centre and the pharmacokinetic (PK) analyses will be done by Parexel and described in a separate document.

3 STUDY OBJECTIVES AND ENDPOINTS

3.1 Primary Objective

The primary objective is to evaluate the PK and safety profile of multiple ascending dose levels of NT-814, compared to placebo, by once daily administration of each dose for 14 days.

3.2 Exploratory Objectives

The exploratory objectives are as follows:

- To assess effects of multiple, single daily doses of NT-814, compared to placebo, on hot flash frequency and severity using objective and subjective measures.
- To investigate the relationship between PK exposure and hot flash measures, if data permit.
- To explore the relationship between plasma concentrations and placebo-corrected change from baseline QTcF and QTcB values using concentration effect modeling, depending on the results observed.

3.3 Pharmacokinetic Endpoints

The PK endpoints include:

- peak concentration (C_{\max})
- time of occurrence of C_{\max} (T_{\max})
- area under the curve (AUC) from time zero to the time of the last quantifiable concentration (AUC_{0-t})
- AUC in the dosing interval ($AUC_{0-\tau}$, synonymous with AUC_{0-24})
- AUC from time zero extrapolated to infinity ($AUC_{0-\infty}$)
- apparent terminal phase half-life ($t_{1/2}$)
- apparent clearance (CL/F)

The PK parameters will be derived on Day 1, Day 7, and Day 14, as appropriate.

3.4 Safety Endpoints

The safety endpoints are as follows:

- Physical examinations

- Analysis for arrhythmias by continuous Holter monitoring from Day -1 to Day 8 and Day 14 (24 hours)
- Abnormalities on 12-lead electrocardiograms (ECGs)
- Change from baseline in ECG variables (heart rate [HR], RR, PR, QRS, QT, QTcF, and QTcB)
- Change from baseline in clinical laboratory assessments, including lipids and coagulation profile
- Change from baseline in hormones including estradiol, testosterone, follicle stimulating hormone (FSH), adrenocorticotrophic hormone (ACTH), cortisol, thyroid-stimulating hormone (TSH), triiodothyronine (T3), and thyroxine (T4)
- Change from baseline in vital signs including oxygen saturation, oral temperature, and postural blood pressure (BP) changes
- Adverse events (AEs) of dehydration (supported by changes in serum urea and creatinine, urinary sediment and weight and vital signs)
- Nature and severity of AEs
- Withdrawals due to an AE

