8.2 Safety endpoints

Safety and tolerability will be assessed by the following:

- Physical Examinations
- Analysis for arrhythmias as assessed by continuous Holter monitoring from Day -1 to Day 8 (24 hours post Day 7 dose) and Day 14 (24 hours)
- Abnormalities on the 12-lead ECGs
- Change in ECG variables (heart rate, RR, PR, QRS, QT, QTcF and QTcB)
- Change from Baseline in clinical laboratory assessments including lipids and coagulation profile
- Change from baseline in hormones including estradiol, testosterone, follicle stimulating hormone (FSH), adrenocorticotropic hormone (ACTH), cortisol, thyroid-stimulating hormone (TSH), triiodothyronine (T3) and thyroxine (T4)
- Change from Baseline in vital signs including oxygen saturation, oral temperature and postural blood pressure (BP) changes
- Adverse events (AEs) of dehydration (supported by changes in serum urea and creatinine, urinary sediment and weight and vital signs)
- Nature and severity of Adverse Events (AE)
- Withdrawals due to AEs

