4.10.3 Vital Signs

Vital signs will include sitting and standing BP, HR, arterial oxygen saturation, oral body temperature, respiration rate, and weight. Vital sign assessments will be performed on Day -1 at a similar time to the same assessments that are planned predose on Day 1. The assessments will then be performed postdose for all other days in clinic and at a similar time on Day 15.

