8 STATISTICAL METHODS

8.1 General

The statistical analysis will be conducted following the principles specified in the International Council for Harmonization, formerly the International Conference on Harmonization, Topic E9 Statistical Principles for Clinical Trials (CPMP/ICH/363/96).

All statistical tabulations and analyses will be done using SAS[®], Version 9.3 or higher.

Unless otherwise noted, continuous variables will be summarized using number of non-missing observations, arithmetic mean, standard deviation (SD), median, minimum, and maximum; categorical variables will be summarized using the frequency count and the percentage of subjects in each category.

In the data listings, study day relative to first dose of study drug may be presented. Study day relative to first dose will be calculated as: event date – first dose date (+ 1 if event date \geq first dose date). That is, there is no Day 0.

Baseline will be the latest available measurement prior to the first study drug administration in the study, unless otherwise specified.

For safety summaries, the unscheduled and repeat assessments will not be summarized; however, all results will be included in the data listing.

All subject level data, including those derived, will be presented in the individual subject data listings.

Unless otherwise noted, the analyses will be done by treatment (50 mg NT-814, 100 mg NT-814, 150 mg NT-814, etc... (XX mg NT-814), Total NT-814 (if applicable), placebo). Data for the placebo subjects will be combined across cohorts prior to any summaries.

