8.11.4 Vital Signs

Vital signs data will be listed by subject at each time point. Observed and change from baseline vital signs values (pulse rate, respiration rate, arterial oxygen saturation, systolic and diastolic BP, oral temperature, and weight) will be summarized by treatment at each time point period.

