Figure 14.2.1.5.1	Mean (+/- SE) Night Time Awakenings (Total) - Twice Daily Diary (Full Analysis Set)
Figure 14.2.2.1.1	Mean (+/- SE) Daily Frequency of Hot Flashes - Continuous Hot Flash Diary (Full Analysis Set)
Figure 14.2.2.2.1	Mean (+/- SE) Night Time Awakenings Secondary to Hot Flashes

	- Continuous Hot Flash Diary (Full Analysis Set)
Figure 14.2.2.3.1	Mean (+/- SE) Night Time Awakenings (Total) - Continuous Hot Flash Diary (Full Analysis Set)
Figure 14.2.3.1	Mean (+/- SE) Daily Frequency of Hot Flashes Detected by the Device - Sternal Skin Conductance (Full Analysis Set)
Section 14.3	Safety Data Summaries
Section 14.3.1	Displays of Adverse Events
Table 14.3.1.1	Overall Summary of Treatment-Emergent Adverse Events (Safety Set)
Table 14.3.1.2	Summary of Treatment-Emergent Adverse Events by System Organ Class and Preferred Term (Safety Set)
Table 14.3.1.3	Summary of Treatment-Emergent Adverse Events by Reported Severity (Safety Set)
Table 14.3.1.4	Summary of Treatment-Emergent Adverse Events by Relationship to Study Drug (Safety Set)
Section 14.3.2	Listings of Deaths, Other Serious and Certain Significant Adverse Events
Table 14.3.2.1	Listing of Adverse Events Leading to Death (Safety Set)
Table 14.3.2.2	Listing of Serious Adverse Events (Safety Set)
Table 14.3.2.3	Listing of Adverse Events Resulting in Discontinuation of Study or Treatment (Safety Set)
Table 14.3.2.4	Listing of Treatment-Emergent Adverse Events of Dehydration (Safety Set)
Section 14.3.4	Abnormal Laboratory Value Listing
Table 14.3.4.1	Listing of Abnormal Laboratory Results (Safety Set)
Section 14.3.5	Additional Safety Data Summaries
Table 14.3.5.1	Absolute and Change from Baseline for Clinical Laboratory Parameters (Chemistry, Hematology, Lipids and Coagulation)

	(Safety Set)
Table 14.3.5.2	Absolute and Change from Baseline for Laboratory Hormones Results (Safety Set)
Table 14.3.5.3	Laboratory Shift in Normal Range Indicator by Category (Chemistry, Hematology, Lipids and Coagulation) (Safety Set)
Table 14.3.5.4	Laboratory Shift in Normal Range Indicator of Hormones Results (Safety Set)
Table 14.3.5.5	Absolute and Change from Baseline Vital Signs (Safety Set)
Table 14.3.5.6	Summary Statistics of 12-Lead ECG Values and Change from Baseline (Safety Set)
Table 14.3.5.7.1.1	Summary of Daily Maximum QTcB and QTcF Interval Results (Safety Set)
Table 14.3.5.7.1.2	Summary of Overall Maximum Post-Baseline QTcB and QTcF Interval Results (Safety Set)

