Listing 16.2.6.1.3.3	Skin Conductance Monitor Hot Flashes Detected by the Device - Derivation (Full Analysis Set)
Listing 16.2.6.1.4	Luteinizing Hormone Data (Full Analysis Set)
Section 16.2.7	Adverse Event Listings
Listing 16.2.7.1	All Adverse Events (Safety Set)
Listing 16.2.7.2	Verbatim to Preferred Term Mapping of All Adverse Events
Section 16.2.8	Individual Laboratory Measurements by Subject
Listing 16.2.8.1	Normal Ranges for Laboratory Data
Listing 16.2.8.2	Clinical Laboratory Data by Category (Chemistry, Hematology, Lipids and Coagulation) (Safety Set)
Listing 16.2.8.3	Hormones Results (Safety Set)
Listing 16.2.8.4	Urinalysis Results (Safety Set)
Listing 16.2.8.5	Vital Signs (Safety Set)
Listing 16.2.8.6	12-Lead Electrocardiogram Results (Safety Set)
Listing 16.2.8.7	Holter Electrocardiogram Monitoring (Safety Set)
Listing 16.2.8.8	Physical Examination (Safety Set)
Listing 16.2.8.9	Investigator Comments (Safety Set)

VERSION HISTORY

Version	Date	List principal changes from previous version
2.0	27FEB2017	
- Section 4.1 and 4.10.5 has been changed to take into account the changes in the protocol version 4.0 dated 13DEC2016.- The night time awakenings analyses are now separated in 2 groups: NTA secondary to hot flashes and NTA, Total- The baseline for ECG is now defined as the time matched assessment done at Day -1- The maximum QTcB and QTcF values are analysed daily and overall.
1.0	01DEC2016	NA. Initial Version

STATISTICAL ANALYSIS PLAN FOR PHARMACOKINETICS

Protocol RELENT-1

EVALUATION OF THE PHARMACOKINETICS AND SAFETY OF NT-814 IN POST-
MENOPAUSAL WOMEN WITH VASOMOTOR SYMPTOMS

Version: Final 1.0

Date: 5 May 2017

REVISION HISTORY

[figure not shown]
Version	Version Date	Author	Summary of Changes Made
Draft 1.0	April 10, 2017	PPD	New Document
Final 1.0	May 5, 2017	PPD	

SIGNATURE PAGE - NERRE THERAPEUTICS LTD.

Declaration

The undersigned has/have reviewed and agree to the statistical analyses and procedures of this clinical study, as presented in this document.

PPD

Date (DD Mmm YYYY)

8th May 2017

[figure not shown]
Date (DD Mmm YYYY)

SIGNATURE PAGE - NERRE THERAPEUTICS LTD.

Declaration

The undersigned has/have reviewed and agree to the statistical analyses and procedures of this clinical study, as presented in this document.

PPD

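### Postural BP change is a named part of the vital-signs safety endpoint, but SAP 8.11.4 derives no standing-minus-sitting variable, so it has no planned by-treatment summary

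*SAP*

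**What the plan says.** **Endpoint.** Protocol 8.2 lists "Change from Baseline in vital signs including oxygen saturation, oral temperature and postural blood pressure (BP) changes" among the safety endpoints. SAP 3.4 carries it over as "Change from baseline in vital signs including oxygen saturation, oral temperature, and postural blood pressure (BP) changes".

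**Collection.** SAP 4.10.3 states: "Vital signs will include sitting and standing BP, HR, arterial oxygen saturation, oral body temperature, respiration rate, and weight". Protocol 10.4.9 and footnote 3 to Protocol Table 2 also specify both postures.

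**Analysis.** SAP 8.11.4 plans a listing and a summary by treatment and time point of "Observed and change from baseline vital signs values (pulse rate, respiration rate, arterial oxygen saturation, systolic and diastolic BP, oral temperature, and weight". SAP 8.1 sets the default statistics: "continuous variables will be summarized using number of non-missing observations, arithmetic mean, standard deviation (SD), median, minimum, and maximum". The output list in SAP Section 9 has one vital-signs summary, Table 14.3.5.5, "Absolute and Change from Baseline Vital Signs (Safety Set", and one by-subject listing, 16.2.8.5.

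**Timing.** After placing the Day -1 reading at the planned Day 1 predose time, SAP 4.10.3 continues: "The assessments will then be performed postdose for all other days in clinic and at a similar time on Day 15". Footnote 3 to Protocol Table 2 instead puts the other in-clinic readings about half an hour before the dose.

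**The concern.** The endpoint promises a quantity that the analysis section never constructs. A postural change is a within-woman difference between two readings at the same assessment. SAP 8.11.4 names no such difference and does not say which posture its BP values refer to.

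Safety compared with placebo is half of the primary objective, and the safety analysis is descriptive with no primary hypothesis test (Protocol 11). The tables are therefore the result. Vital signs are also a stated support for the dehydration endpoint, and Protocol 9.8 gives orthostatic hypotension as an example of a dehydration sign that requires stopping study drug. If the SAP is followed as written, the study report can describe oxygen saturation and temperature by dose against pooled placebo, but not the third measure that the endpoint names. Any postural summary added later would have its definition chosen after the data had been seen.

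**Working it through.** The plan states no figure on this point, so there is nothing to reproduce. The check compares texts and adds one line of algebra.

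**Step 1. Match the endpoint to the analysis list.**

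| Measure named in Protocol 8.2 and SAP 3.4 | Collected? | In the SAP 8.11.4 list? |
|---|---|---|
| Oxygen saturation | Yes | Yes |
| Oral temperature | Yes | Yes |
| Postural BP change | Yes, as paired sitting and standing BP | No |

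The SAP 8.11.4 list holds 7 variables: pulse, respiration, oxygen saturation, systolic BP, diastolic BP, temperature and weight. None carries a posture and none is a difference between postures. Two of the three named measures are covered.

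**Step 2. Look for the derivation elsewhere.** In the main SAP, postural change is mentioned only in the endpoint list. Section 9 has no postural or orthostatic table. SAP 8.1 says that derived subject-level data will be listed, but no postural variable is defined, so none would be listed.

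**Step 3. Ask what posture labels alone would give.** Suppose Table 14.3.5.5 shows sitting and standing rows. For each woman let D = standing − sitting.

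- Mean(D) = mean(standing) − mean(sitting), provided the same women contribute to both rows. The mean is recoverable by subtraction, and so is the mean change from baseline in D.
- Var(D) = Var(standing) + Var(sitting) − 2 × Cov(standing, sitting). SAP 8.1 supplies the two variances through the SDs, but not the covariance. The spread of D is not recoverable.
- The largest individual fall is the minimum of D. The sitting and standing minima need not come from the same woman, so the printed minima and maxima do not give it.

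This follows whatever the BP values are, so no SD or correlation has to be assumed.

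**Step 4. Where the pairs remain.** Only Listing 16.2.8.5 keeps the two readings of one woman together. Under footnote 3 to Protocol Table 2, assessments after the first dose fall on Days 2 to 8 (7), Day 14 (1) and Day 15 (1): 7 + 1 + 1 = 9. With five full cohorts this is 100 × 9 = 900 pairs. With the four cohorts described in Section 3 of the PK SAP it is 80 × 9 = 720. Both are upper limits, assuming no missed assessments. They show how much a reader would have to work through by hand; they do not measure harm.

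**Step 5. Timing text.** The protocol has readings about 30 minutes before dosing on the other clinic days, which is roughly 24 hours after the previous once-daily dose, so they are trough readings. SAP 4.10.3 calls them postdose. SAP Section 5 declares conduct consistent with Protocol Version 4.0 and discloses only the dropped QTcB exposure-response analysis.

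**The case against.** The strongest reply is that posture is implicit. SAP 4.10.3 defines vital signs to include BP in both positions, and SAP 8.11.4 summarises vital signs, so a programmer would naturally produce rows for each posture. Nothing says that the postures are pooled or that one is dropped. This is fair, and a reader should not infer pooling. It rescues only the mean postural change, however (Step 3).

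Second, other outputs give some cover. A woman with signs of dehydration, for example orthostatic hypotension, must stop drug under Protocol 9.8. If this is recorded as an AE, it enters the TEAE and discontinuation outputs. That stands, but SAP 8.11.2 limits the dehydration TEAE summary to changes that the investigator classifies as an AE. A measured fall not so classified reaches no summary.

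Third, a reader might infer that dose escalation is weakened. The documents do not support that. None of the stopping criteria in Protocol 9.9 is defined on a sitting-to-standing change; for symptomatic hypotension, criterion 5 uses resting supine SBP. The individual stopping rule in Protocol 9.8 does not depend on a table either.

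Fourth, a reader might infer that the endpoint requires a count of women with an orthostatic fall. Neither document states a threshold, so such a count is optional.

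Fifth, a reader might take the timing conflict to mean that readings will be taken after dosing or that an analysis changes. The protocol governs conduct, and SAP 4.10.3 describes assessments. It is an error of restatement that changes no baseline, estimate or table content.

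**Conclusion.** The point holds as an omission. One of three measures named in the vital-signs safety endpoint has no planned by-treatment summary, although the data to build it are collected. If the two postures are shown separately, the gap narrows to the spread and the individual falls; if they are not, the mean is missing as well. Confidence in the omission is high because it rests on the text and on the algebra of a difference, not on assumed values.

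The consequence is limited. The data stay in the listing, and nothing in the documents shows that a postural effect exists, how large it might be, or that a safety conclusion would be wrong. It should be corrected because the study cannot otherwise report its own endpoint, but it does not threaten the conduct of the trial. The predose/postdose mismatch is secondary. It matters only if the report repeats the SAP wording, in which case trough readings would be taken to cover the hours after dosing.

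**What to change.** In SAP 8.11.4:

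- Summarise sitting and standing SBP and DBP separately.
- Define postural change as standing minus sitting, for SBP and for DBP, at each assessment where both readings exist.
- Summarise observed postural change and its change from baseline by treatment and time point in Table 14.3.5.5, using the SAP 8.1 statistics and the SAP 8.1 baseline rule.

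In SAP 4.10.3, as a wording correction only, replace the word postdose with the protocol's timing of about 30 minutes before the dose.

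The cost is two derived variables, a few more table rows and one corrected line. All the data are already collected; no protocol amendment and no new assessment are needed. The only downside is a longer vital-signs table. Making the change before unblinding fixes the definition in advance.
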